3.3 Operationalisation of Core Variables and Measurement Time Points

3.3.1 Independent variables

Core independent variables include: (1) intervention allocation (smart RT intervention group vs. health education control group), the primary independent variable; (2) baseline

demographic and clinical characteristics (age, sex, education, BMI, T-score, fracture history, comorbidities), serving as covariates; (3) technology acceptance indicators, assessed via the eHLQ and TAM scales; and (4) intervention process indicators—adherence (proportion of sessions completed) and dose (cumulative training volume).

3.3.2 Dependent variables

Primary outcomes: (a) BMD (g/cm^2) measured by DXA at the lumbar spine, reported as absolute values and percentage change from baseline; (b) physical function assessed by SPPB total score (0–12), 4-metre gait speed (m/s), and five-times sit-to-stand test (seconds); (c) QoL assessed by SF-36 physical component summary (PCS) and mental component summary (MCS) scores (0–100).

Secondary outcomes: fall incidence (monthly fall diaries and telephone follow-up), Falls Efficacy Scale–International (FES-I, 16–64), grip strength (HGS, kg), and visual analogue scale for pain (VAS, 0–10). Supplementary assessments include TUG, Berg Balance Scale, and the Chinese Osteoporosis Screening Scale (SSS-CN).

Mechanistic indicators: ΔHGS (change in grip strength from baseline to 8 months), analysed as a mediator of BMD improvement.

3.3.3 Covariates and potential confounders

The following covariates will be controlled in the analysis: (a) osteoporosis medication use (type and adherence); (b) comorbidity burden (number of chronic conditions); (c) nutritional and metabolic indicators (calcium and vitamin D intake adequacy); and (d) baseline physical activity level (IPAQ, MET-min/week).

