4.4 Primary and Secondary Outcome Measures

4.4.1 Primary outcomes (T2)

BMD: Lumbar spine BMD (g/cm^2) measured by DXA (e.g., GE Lunar Prodigy), reported as absolute values and percentage change from baseline. Within-day coefficient of variation for lumbar spine BMD is approximately 1%.

Physical function: SPPB total score (0–12), comprising standing balance, 4-metre gait speed, and five-times chair-stand subtests (each scored 0–4).

Quality of life: SF-36 Physical Component Summary (PCS) and Mental Component Summary (MCS), each scored 0–100.

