4.5.3 Data cleaning

Missing data: distributions and patterns are reported for all key variables. Little's MCAR test assesses missingness mechanisms; if data are missing at random (MAR), multiple imputation is used for sensitivity analysis. Linear mixed models in the primary analysis accommodate incomplete data. Outliers: identified through distribution plots and box plots, verified against original records, and handled according to pre-specified rules: confirmed errors are corrected, physiologically implausible values are excluded, and plausible extreme values are retained with

robust or sensitivity analyses (e.g., Winsorisation). All exclusions and modifications are documented.

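### The named covariates leave out the T0 value of SPPB, PCS and MCS; the protocol should secure baseline adjustment for each primary outcome

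*Protocol*

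**What the plan says.** Two places in the protocol name covariates. Section 3.3.1 lists, among the core independent variables, "demographic and clinical characteristics (age, sex, education, BMI, T-score, fracture history, comorbidities), serving as covariates". Section 3.3.3 states "The following covariates will be controlled in the analysis: (a) osteoporosis medication use (type and adherence); (b) comorbidity burden (number of chronic conditions"), followed by "c) nutritional and metabolic indicators (calcium and vitamin D intake adequacy); and (d) baseline physical activity level (IPAQ, MET-min/week").

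Section 4.4.1 sets the primary outcomes at T2:
- lumbar spine BMD, "measured by DXA (e.g., GE Lunar Prodigy), reported as absolute values and percentage change from baseline";
- "SPPB total score (0–12), comprising standing balance, 4-metre gait speed, and five-times chair-stand subtests (each scored 0–4");
- "SF-36 Physical Component Summary (PCS) and Mental Component Summary (MCS), each scored 0–100".

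Section 3.3.2 has a longer primary list for function: "physical function assessed by SPPB total score (0–12), 4-metre gait speed (m/s), and five-times sit-to-stand test (seconds").

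The schedule in section 3.3.4 has SPPB, gait speed, five-times sit-to-stand and SF-36 at T0, T1, T2 and T3. On the model, section 4.5.3 says only "Linear mixed models in the primary analysis accommodate incomplete data".

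**The concern.** For a continuous outcome measured before and after treatment, the baseline value of that outcome is normally the strongest predictor of its later value. The protocol names ten distinct covariates, and the only one tied to a primary outcome is T-score. T-score bears on BMD alone, and its site is not given; section 4.2.1 accepts either a lumbar spine or a hip T-score for eligibility.

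If SPPB, PCS and MCS were analysed with the named covariates and nothing more, their confidence intervals would be wider than the collected data allow. Chance differences between the arms at T0 would also pass into the T2 estimate. Section 4.2.3 describes a computer-generated sequence and mentions no stratification, so nothing in the allocation guards against such differences.

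**Working it through.** **Plan's own figure.** The protocol supplies no sample size, SD, correlation or power for these outcomes, so there is no stated figure to reproduce.

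**Count of covariates.** Section 3.3.1 gives 7 and section 3.3.3 gives 4: 7 + 4 = 11 entries. Comorbidities appear in both, so 11 − 1 = 10 distinct, which is T-score plus nine. None is the T0 value of SPPB, PCS, MCS, gait speed or five-times sit-to-stand.

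**What the mixed model can estimate at T2.** Take outcome SD 1 at T0 and T2, correlation ρ, and n per arm.

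| How T0 enters | T2 contrast | Variance factor |
|---|---|---|
| Not used | Final values | 1 |
| Response, free group means at T0 | Change scores | 2(1 − ρ) |
| Covariate, or response with a common mean at T0 | Baseline-adjusted | 1 − ρ² |

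The standard error is √(2 × factor / n). A generalised least squares calculation with 45 per arm confirms the table:
- ρ = 0.5: the common-mean mixed model gives √(2 × 0.75/45) = 0.183, the same as covariate adjustment. Free group means give √(2 × 1.00/45) = 0.211, the same as change scores.
- ρ = 0.7: 0.151 for the common-mean model, 0.163 with free means and 0.211 for final values.

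The variance of change scores relative to the adjusted analysis is 2/(1 + ρ): 1.54 at ρ = 0.3, 1.33 at 0.5, 1.18 at 0.7 and 1.11 at 0.8.

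**Chance imbalance.** Given a T0 difference Δ between arms, the final-value contrast shifts by ρΔ on average, and the change-score contrast by −(1 − ρ)Δ. The adjusted contrast does not shift. At ρ = 0.5 the first two each carry half of Δ.

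**Power.** Two-sided 5% two-sample t test, noncentral t, with one degree of freedom removed for adjustment. The assumed inputs are:
- effect 0.5 SD;
- 40 or 49 per arm; section 1.4.4 mentions n < 100, but for the sub-study 2 dose–response model, so this is not the trial's stated size;
- ρ from 0.3 to 0.8.

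| n per arm | ρ | Final values | Change scores | Adjusted |
|---|---|---|---|---|
| 40 | 0.3 | 59.8% | 46.3% | 63.9% |
| 40 | 0.5 | 59.8% | 59.8% | 72.2% |
| 40 | 0.7 | 59.8% | 81.4% | 87.1% |
| 40 | 0.8 | 59.8% | 93.7% | 95.7% |
| 49 | 0.5 | 68.8% | 68.8% | 80.8% |

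At ρ = 0.5 the difference is 72.2 − 59.8 = 12.4 points with 40 per arm and 80.8 − 68.8 = 12.0 with 49. Against change scores with 40 per arm it is 87.1 − 81.4 = 5.7 points at ρ = 0.7 and 95.7 − 93.7 = 2.0 at ρ = 0.8. Against final values it is 63.9 − 59.8 = 4.1 points at ρ = 0.3.

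At 0.63 SD, the SPPB effect cited in section 1.3.2 for machine-based training, ρ = 0.5 gives 79.5% against 89.5% with 40 per arm, and 87.0% against 94.6% with 49.

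These figures ignore the listed covariates. Age and comorbidity explain some of baseline SPPB, so the real gain would be smaller by an amount the protocol does not let one calculate.

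**The case against.** The strongest reply is that the two lists are not a model specification. Section 3.3.1 belongs to a catalogue of variables that also holds eHLQ, TAM, adherence and dose, and it serves six sub-studies. Section 3.3.3 speaks of the analysis without naming a model or an endpoint. Neither list is declared complete. In a mixed model T0 may be a response, so its absence from a covariate list proves nothing, and how T0 enters is often settled in a SAP, which is not at hand.

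Most of this stands. A reader might infer that every analysis is fixed without baseline outcome values and that power is therefore lost on three of four primary endpoints. The documents do not support that. They do not make the lists exhaustive, and a mixed model with a common T0 mean loses nothing. The count of three of four also holds only under section 4.4.1; section 3.3.2 lists six primary measures.

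What the reply does not remove is that the protocol chose to name its covariates in firm terms, and nothing in it secures adjustment for the T0 outcome value. A SAP that simply followed the lists, with free T0 means or without T0, would arrive at one of the less precise contrasts. Adding the missing terms improves a stated set; it is not a request for detail the protocol never touched.

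A reader might also infer that percentage change in BMD should become merely descriptive. That does not follow from the missing SPPB, PCS and MCS baselines, and it would cut across the objective of at least 3% in section 1.4.1.

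**Conclusion.** The point holds conditionally. The named covariates omit the T0 values of SPPB, PCS and MCS, and of gait speed and five-times sit-to-stand where section 3.3.2 makes them primary, although all are measured at T0. Precision and protection against chance imbalance are kept only if the mixed model adjusts for T0 or constrains the T0 means to be equal, and the protocol states neither.

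The loss otherwise is anywhere from about 2 points to well above 12, depending on the correlation and on which contrast results; about 12 points is the figure for the central assumptions. Sample size, correlation and effect are all assumed, only two time points are used, and the listed covariates are left out of the calculation. This is a worthwhile improvement at almost no cost, not an error that invalidates the analysis.

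**What to change.** In sections 3.3.1 and 3.3.3, state that each primary-outcome model adjusts for the T0 value of that same outcome: SPPB for SPPB, PCS for PCS, MCS for MCS, and lumbar spine BMD in g/cm² for BMD. Do the same for gait speed and five-times sit-to-stand if they remain primary. Say which form is used: T0 as a covariate in a model of the later values, or T0 as a response with one mean common to both arms. Report the adjusted between-group difference at T2. Leave the reporting of percentage change in BMD as it is.

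The cost is about one sentence and one degree of freedom per model. The T0 measurements are already scheduled, so no participant, visit or staff time is added. Settling it before unblinded data are seen also removes any later choice among final-value, change-score and adjusted results.

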3.3.4 Detailed measurement schedule

表 3.3.4 Data measurement schedule 数据测量时间表						
Measurement field 测量领域	Specific measurement items 具体测量项目	T0	T1	T2	T3	备注
		Before intervention 干预前	4 months 4 个月	8 months 8 个月	14 months 14 个月	
Demography 人口学	Age, gender, education level, medical history, medication use	✓				Baseline collection only
Physical indicators	Height, weight, BMI	✓		✓	✓	Tracking changes

身体指标						
BMD 骨密度 DXA	Lumbar spine and hip BMD	✓	✓	✓	✓	4 months DXA As needed
Body functions 身体功能	SPPB Overall Rating	✓	✓	✓	✓	
	Overall balance	✓	✓	✓	✓	
	4-meter pace	✓	✓	✓	✓	
	5 Sit-to-Stand (5STS)	✓	✓	✓	✓	
	Grip strength (HGS)	✓	✓	✓	✓	Intermediary Indicators
Questionnaire 问卷调查	SF-36	✓	✓	✓	✓	
	FES-1	✓	✓	✓	✓	
	eHLQ、TAM	✓	✓	✓		Track
Implementation process 实施过程	Training compliance and dosage (platform log and manual log)		✓	✓		Continuous recording to stage nodes
Safety Monitoring 安全监测	Cumulative number of falls & adverse events			✓	✓	Summary
	New fracture				✓	
Behavior Tracking 行为追踪	Daily physical activity after intervention				✓	

Measurements are conducted at four time points: T0 (baseline, 1 week pre-randomisation) includes comprehensive demographic, clinical, functional, and questionnaire assessments; T1 (mid-intervention, 4 months) comprises streamlined assessments covering DXA (resources permitting), functional tests, adherence data, and questionnaires; T2 (end of intervention, 8 months) repeats the full baseline assessment battery plus cumulative adverse events; and T3 (follow-up, 20 months) evaluates long-term outcomes including new fractures, BMD maintenance, and post-intervention physical activity.

Chapter 4 Overall Methodology and Ethics

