1.3.4 Key evidence gaps that this study aims to address

Drawing on the foregoing analysis of demographic change, OP burden, RT mechanisms, and existing evidence limitations, this study targets six principal evidence gaps, aiming to construct a scientifically grounded, implementable, and scalable “community-based smart RT intervention model.”

First, the absence of long-term intervention evidence. This study will employ a 20-month tracking design comprising an 8-month active training phase and a 12-month maintenance phase, with systematic observation of BMD and muscle-strength trajectories, particularly among subgroups aged ≥ 75 years and those with a Fried Frailty Index ≥ 3 .

Second, insufficient evidence for community scalability. The study will adopt a “low-equipment-dependency” model centred on elastic-band and bodyweight training modules suitable for home or community settings, supported by a three-tier management hierarchy (professionals–community volunteers–family mutual support) and standardised illustrated and video-guided protocols.

Third, low adherence as a barrier. The study will integrate AI-enabled monitoring (smart wristbands), gamification (reward and incentive systems), and peer supervision to enhance participation, targeting an adherence rate exceeding 70%.

Fourth, the absence of cost-effectiveness data. A health-economics evaluation framework will be established, introducing Markov modelling to community RT research for the first time, to quantify the incremental cost-effectiveness ratio (ICER) and cost–utility ratio (CUA), benchmarked against pharmacological interventions such as zoledronic acid.

Fifth, the lack of smart support-system integration. The study will design a “four-dimensional linked” system architecture encompassing data acquisition (wearable terminals), intelligent analytical feedback (AI algorithm platform), community-setting application (elderly care stations or activity centres), and family interaction mechanisms, with emphasis on age-friendly design including voice guidance, offline functionality, and simplified interfaces.

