1.4 Research Objectives and Innovations

1.4.1 Overall research objective

The overarching objective is to validate the comprehensive benefits of “community-based

smart RT” for BMD, muscular function, and quality of life (QoL) among older adults with OP, and to establish a sustainable implementation pathway. Specifically: (a) quantify the effect of 8-month RT on lumbar spine BMD through an RCT, with an expected increase of $\geq 3\%$ (benchmarked against the IOF clinical significance threshold); (b) design a long-term intervention strategy with 8 months of supervised training (twice weekly) followed by 12 months of low-frequency maintenance (once monthly); and (c) develop an integrated smart elderly care system featuring real-time wearable monitoring, AI-driven exercise prescription adjustment, and community-station offline supervision, achieving “data–professional–family” three-tier coordination.

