4.2 Participants

4.2.1 Inclusion criteria

Eligible participants must: (1) be aged ≥ 60 years (either sex); (2) have a DXA-confirmed diagnosis of primary OP (lumbar spine or hip T-score ≤ -2.5 , or ≤ -2.0 with a fragility fracture history); (3) reside in the designated community with no relocation plans within one year; (4) demonstrate adequate cognitive function (MMSE ≥ 24 , adjusted for education level); (5) be

independently ambulatory (assistive devices permitted; severe motor impairments excluded); (6) provide written informed consent; and (7) have confirmed primary OP (secondary OP excluded).

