4.2.2 Exclusion criteria

Exclusion criteria include: (1) recent major medical events (fracture, hip/spine surgery within 3 months, or uncontrolled cardiovascular disease within 6 months); (2) current participation in comparable exercise programmes or clinical trials; (3) terminal illness with estimated survival <1 year; (4) inability to complete 12-month follow-up (planned relocation); (5) severe sensory or communication impairments precluding training participation; (6) other conditions deemed unsuitable by investigators (e.g., severe alcohol dependence); and (7) lack of family/caregiver support.

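### Protocol section 3.3.4 gives the T3 visit two dates, 14 months in the schedule table and 20 months in the text beneath it

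*Protocol*

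**What the plan says.** The table in Protocol section 3.3.4 has four time columns. T0 is before the intervention, T1 is at 4 months and T2 at 8 months. The T3 column is headed "14 months 14 个月". The paragraph below the table agrees with it on T0 to T2 but then states: "T3 (follow-up, 20 months) evaluates long-term outcomes including new fractures, BMD maintenance, and post-intervention physical activity".

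Two earlier sections bear on the length of the study. Section 1.3.4 describes a "20-month tracking design comprising an 8-month active training phase and a 12-month maintenance phase". Section 1.4.1 describes 8 months of supervised training "followed by 12 months of low-frequency maintenance (once monthly"). It gives the two phase lengths but neither a total nor a T3 date.

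Eligibility works to a shorter horizon. Inclusion criterion 3 (section 4.2.1) asks candidates to "reside in the designated community with no relocation plans within one year". Exclusion criterion 4 (section 4.2.2) is "inability to complete 12-month follow-up (planned relocation").

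In the table, new fractures and daily activity after the intervention are ticked at T3 only. BMD, SPPB and SF-36 are ticked at all four visits, and training compliance and dosage at T1 and T2 only. Section 4.4.1 fixes the primary outcomes at T2.

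**The concern.** A visit can have only one planned date, and here the table and its own explanatory paragraph disagree. Whoever follows one departs from the other.

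What depends on the date is everything the trial will know about the period after T2. In the table's version T3 falls midway through the 12-month maintenance phase; in the text's version it falls at the end. BMD retained 6 months after training and BMD retained 12 months after training are different quantities. Counts of fractures and cumulative falls would also cover different lengths of observation.

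Two related matters affect how T3 can be read. The eligibility criteria appear to screen for relocation over 12 months, which is short of T3 on either date. And the schedule records no training compliance after T2, although section 1.4.1 describes monthly maintenance sessions in that period.

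**Working it through.** This is calendar arithmetic on figures in the Protocol.

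**Inputs**

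| Item | Value | Source |
|---|---|---|
| End of intervention, T2 | 8 months | 3.3.4, table and text |
| Active training phase | 8 months | 1.3.4, 1.4.1 |
| Maintenance phase | 12 months | 1.3.4, 1.4.1 |
| Total tracking | 20 months | 1.3.4 |
| T3, table | 14 months | 3.3.4 |
| T3, text | 20 months | 3.3.4 |
| Relocation and follow-up horizon | 12 months | 4.2.1, 4.2.2 |

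**Step 1. Reproduce the stated total.** Active + maintenance = 8 + 12 = 20 months. This agrees with section 1.3.4 and with the T3 date in the text.

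**Step 2. Try to reach 14.** 14 = 8 + 6, but no 6-month phase is described. Counting 14 months from T2 gives 8 + 14 = 22; counting 20 months from T2 gives 8 + 20 = 28. No choice of origin makes the two dates agree.

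**Step 3. Consequence for T3.**
- Time since the end of training: 14 − 8 = 6 months, or 20 − 8 = 12 months.
- Position in the maintenance phase: 6/12 = half way, or 12/12 = the end.
- Observation from baseline: 14/20 = 0.70, so the table's version has 30% less time for fractures and falls.

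**Step 4. Eligibility horizon, counted from enrolment.**
- Against T2: 12 − 8 = 4 months to spare.
- Against T3 in the table: 14 − 12 = 2 months short.
- Against T3 in the text: 20 − 12 = 8 months short.

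**Step 5. Maintenance or cessation.** Section 1.4.1 has participants continuing at low frequency for 12 months after T2. Section 3.3.4 calls T2 the end of intervention and refers to activity at T3 as post-intervention. Section 4.3 sets out no separate maintenance phase. With compliance scheduled only at T1 and T2, the trial would hold no attendance data to show which description fits.

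**The case against.** The best reply is that little of the trial rests on T3. The primary outcomes are at T2, hypotheses H1 to H6 are not tied to T3, and long-term evidence is one of several gaps listed in section 1.3.4. A reader might infer that a named maintenance endpoint has been left undefined. The documents do not support that: sections 3.3.2, 4.4.1 and 4.4.2 list no such endpoint among the primary or secondary outcomes. What has two values is the date of a visit.

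Falls are collected by monthly diary and telephone and summarised as an incidence rate ratio, which can use actual person-time. A different end date changes the amount of falls data without making the measure meaningless. This stands.

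On eligibility, a reader might infer that someone planning to move in month 13 could supply no T3 data. That goes too far: falls can be reported by telephone, and a mover may stay within reach of the hospital providing DXA. The 12-month follow-up in exclusion criterion 4 might also mean the 12 months after training, which would end at 8 + 12 = 20. The bracketed reference to relocation and the one-year wording of inclusion criterion 3 make a count from enrolment more natural, but the other reading is possible.

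A reader might further infer that staff will split between the two dates, so that T3 data mix them. Nothing in the document shows this. The study runs in one district with DXA on one device, and a single wrong date is more likely.

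Finally, the table does record daily physical activity at T3, so behaviour after T2 is partly captured. Attendance at maintenance sessions is not.

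None of this removes the conflict between 14 and 20 months, which sits within one section of current text. The 14 appears in both English and Chinese, so a text-extraction fault is unlikely.

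**Conclusion.** The point holds for the date of T3. The two dates differ by 6 months, which doubles or halves the time since training ended (12 against 6 months) and changes the observation period from 20 to 14 months. It affects the T3 assessments only: new fractures, post-intervention activity, and the sole post-T2 measurements of BMD, SPPB and SF-36. The 8-month primary analysis is untouched.

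The weight of the document favours 20 months: the text in 3.3.4 and the design in 1.3.4 say so, and the phase lengths in 1.4.1 add up to it. The sponsor still has to settle the date.

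The eligibility mismatch is secondary and concerns retention. It assumes that the 12 months run from enrolment. The protocol gives no dropout or relocation rate, so the resulting loss at T3 cannot be estimated. The missing compliance record after T2 is also secondary, and correcting the T3 date would not resolve it.

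**What to change.** 1. Put one T3 month in both the table heading and the paragraph of section 3.3.4, and check it against sections 1.3.4 and 1.4.1.
2. Align the horizon in inclusion criterion 3 and exclusion criterion 4 with that month, and state that it runs from enrolment.
3. Either extend the training-compliance row of the schedule to T3, so that attendance in the maintenance phase of section 1.4.1 is recorded, or state that T3 measures a post-cessation effect and reconcile section 1.4.1 with that.

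Items 1 and 2 are changes of wording. Ethical approval is still pending (section 4.7.1), so they can be made now at almost no cost. Item 2 makes a few candidates with known relocation plans ineligible. Item 3 costs either continued logging over the maintenance months or a sentence of clarification.
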